9.7.3 Analysis of treatment data

Summary statistics will be provided for the treatment duration, the number of treatments, starting dose and average dose, the number of patients with dose modification (interruption, delay and discontinuation), number of dose modifications, and reasons for dose modifications.

9.7.4 Analysis of primary outcome(s)

The primary analysis of pain response will be summarized in the population of patients with a score >1 (0="no pain") for the baseline measurement of the 'Worst Pain'-item of the BPI-SF. For each post-baseline assessment, the incidence proportion will be provided, along with the exact 95% confidence

interval. Pain response is defined as an improvement of two points from the baseline BPI-SF worst pain score at any post-baseline assessment, which is considered clinically meaningful [17].

Further details will be given in the SAP.

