9.2.6 Representativeness

No further selection than outlined in Sections 9.2.1 – 9.2.3 should be made and patients should be enrolled consecutively in order to avoid any selection bias. With respect to site selection this study could have potential limited representativeness (at convenience sample) as we would be looking for sites with Radium-223 availability (nuclear medicine licensed facility) and experience with prostate cancer management and treatment. Currently, there are 105 nuclear medicine licensed facilities in Germany (August 2014). For sites participating in the study it is planned to include 8 to 10 patients per site.

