9.5 Study Size

Aim of the sample size consideration is to assess the precision of the estimate for the pain response rate (the primary outcome) which is defined by the width of the 95% confidence interval with a given sample size. Assuming that at least 70% of patients will be evaluable for the primary analysis of pain response at a post-baseline assessment and 30% to 70% of patients show a pain response, at least 300 patients have to be included to reach a precision of < 20%. In the following table, the different scenarios are shown for actual pain response ranging from 30% to 70%.

Table 3: Width of the 95% CI for the pain response rate, assuming 210 evaluable patients

Actual pain response	Lower Limit of 95% CI	Upper Limit of 95% CI	Width of 95% CI
0.7	0.638	0.762	0.124
0.65	0.585	0.715	0.13
0.6	0.534	0.666	0.132
0.55	0.483	0.617	0.134
0.5	0.432	0.568	0.136
0.45	0.383	0.517	0.134
0.4	0.334	0.466	0.132
0.35	0.285	0.415	0.13
0.3	0.238	0.362	0.124

300 patients is a realistic estimate to be enrolled in a two-year enrollment period, based on current patient numbers and available sites for the treatment. With this sample size and a pain response rate of 65% a precision of < 20 % can be reached assuming subgroups to be at least of 1/2 of this size (i.e. 105 patients). From a clinical point of view, this precision is regarded as meaningful, taking the variance of pain measurements into account.

Calculations were performed with nQuery 7.

The sample size could be increased if the number of patients not evaluable for pain response proves to be higher than the expected 30%.

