9.7.8 Bias, confounding and effect-modifying factors

In general data collected in this study may suffer from biases (e.g. interviewer bias, either by systematic differences in data recording or different interpretation of information on exposure or outcome for different patients, reporting as well as selection bias). Besides, prospective studies are prone to bias from loss to follow-up or change in data collection methods over time. To decrease the reporting bias source data verification will be performed in at least 10% of the sites. In order to reduce selection bias, a representative sample of sites will be included in the study. Sites will be selected according to several criteria, main criteria for site selection will be: availability of suitable patients and an equal geographical distribution. Investigators should select patients to be documented in the study only based on eligibility according to inclusion and exclusion criteria, i.e. each patient diagnosed with mCRPC and starting treatment for the disease with Radium-223 should be asked for participation in a consecutive manner. No further selection should be applied.

Primary and secondary outcome variables and safety data will be analyzed with regard to different baseline factors. However, unknown and unmeasured risk factors for the outcome variables will exist and might lead to confounding when comparing results in different subgroups and when comparing study results with historical results from clinical studies.

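### The exact 95% CI for the primary pain response rate and the widths in Table 3 leave out between-site variation, which matters if the intra-site correlation is above about 0.02

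*Protocol*

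**What the plan says.** Section 9.7.4 sets the interval for the primary pain response rate: "For each post-baseline assessment, the incidence proportion will be provided, along with the exact 95% confidence" interval. It mentions neither site nor any adjustment for it.

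Section 9.5 rests the sample size on precision, "defined by the width of the 95% confidence interval with a given sample size". It concludes that "at least 300 patients have to be included to reach a precision of < 20" per cent, with the evaluable share given by "Assuming that at least 70% of patients will be evaluable for the primary analysis". Its table is titled "Table 3: Width of the 95% CI for the pain response rate, assuming 210 evaluable patients". The same section adds that a subgroup of 105 patients with a 65% response rate also keeps the width below 20%.

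On the structure of the cohort, section 9.2.6 says: "For sites participating in the study it is planned to include 8 to 10 patients per site". It counts 105 licensed facilities in Germany and concedes that site selection is one of convenience. Section 9.7.8 nevertheless says the sites included will be representative. Section 9.6 puts the site number into the patient code. No interval or model in the protocol uses site: the analysis of covariance in section 9.7.5 names only baseline worst pain.

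**The concern.** Patients enter through sites. Visits and the post-treatment questionnaire follow local routine (sections 9.2.7 and 9.3.1), and response may occur at any post-baseline assessment. The number of chances to respond can therefore vary from site to site, and perhaps analgesic practice as well. If true response rates differ between sites, the variance of the pooled rate exceeds the binomial variance, and a binomial interval is too short.

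Precision of this rate is the only performance claim the study makes, and the rate is meant to describe routine practice in Germany beyond the participating sites. At stake are whether the reported 95% interval has its stated coverage and whether the precision claims in section 9.5 are realistic.

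**Working it through.** **Inputs from the protocol.** 300 enrolled, 70% evaluable, so 210 (9.5). 8 to 10 enrolled per site, so 300/10 = 30 to 300/8 = 37.5 sites (9.2.6). Evaluable per site m = 0.7 × 8 = 5.6 to 0.7 × 10 = 7.

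**Input not in the protocol.** The ICC; assumed range 0 to 0.10. At a 50% rate, the standard deviation of true site rates is √(ICC × 0.25): 0.071 at ICC 0.02, 0.112 at 0.05, 0.158 at 0.10.

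**1. Reproducing Table 3.** The independent-patient Wald formula p ± 1.96·√(p(1−p)/210) gives every limit in the table to three decimals. At p = 0.5 the limits are 0.432 and 0.568, a difference of 0.136 (unrounded 0.1353). The exact (Clopper-Pearson) method that 9.7.4 prescribes gives 0.139 at p = 0.5 and does not match the table. Table 3 therefore has no site term and uses a different method from the planned analysis.

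**2. Design effect.** DE = 1 + (m − 1)·ICC; the width is multiplied by √DE. At p = 0.5, for m = 5.6 to 7:

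| ICC | DE | Width | Effective n |
|---|---|---|---|
| 0 | 1 | 0.135 | 210 |
| 0.01 | 1.05–1.06 | 0.138–0.139 | 198–201 |
| 0.02 | 1.09–1.12 | 0.141–0.143 | 188–192 |
| 0.05 | 1.23–1.30 | 0.150–0.154 | 161–171 |
| 0.10 | 1.46–1.60 | 0.163–0.171 | 131–144 |

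**3. Coverage of the exact interval.** Beta-binomial simulation with 33 sites and Binomial(9, 0.7) evaluable patients per site. At p = 0.5 the exact interval has a mean width of about 0.140 at every ICC. Its coverage is about 96% at ICC 0, 95% at 0.01, 94.5% at 0.02, 92.5% at 0.05 and 90% at 0.10; results at p = 0.65 are similar. The simulated honest widths (2 × 1.96 × SD of the estimate) are about 0.154 at ICC 0.05 and 0.169 at 0.10. Runs with 30 sites of 7 or 35 sites of 6 give 92.2–93.2% and 88.6–90.3% at these two ICCs.

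**4. Overall target.** The Wald width at p = 0.5 reaches 0.20 when DE = (0.20/0.1353)² = 2.19, so ICC = 1.19/(m − 1), or about 0.20 (m = 7) to 0.26 (m = 5.6). Exact limits on the effective n at ICC 0.10 give 0.169 to 0.177, still below 0.20.

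**5. Subgroup statement (105 patients, 65%).** Independent Wald width: 2 × 1.96 × √(0.65 × 0.35/105) = 0.182. Exact: 0.190. The Wald width passes 0.20 when DE = (0.20/0.1825)² = 1.20:
- subgroup concentrated in some sites (5.6 to 7 per site): ICC 0.20/(m − 1), about 0.034 to 0.044;
- subgroup spread over all sites (2.8 to 3.5 per site): ICC about 0.08 to 0.11.

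With exact limits on the effective n, the crossing points drop to about 0.02 and 0.045 to 0.06.

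**6. Finite number of sites.** Taking 30 to 38 of 105 facilities as a finite sample cuts the between-site part by about 29–36%. With 33 sites and m = 6.3, DE ≈ 1 + 5.3 × ICC × (1 − 33/105). This gives widths of about 0.147 at ICC 0.05 and 0.158 at ICC 0.10.

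**The case against.** The protocol offers no evidence of a material ICC. The endpoint is a within-patient change on a self-completed item, recorded on paper forms that the CRO enters, so site recording habits should affect it little. Treatment is expected to follow the label, and other physicians may manage a patient's analgesia. The study is descriptive, with no test or threshold, and the SAP could add a site-adjusted interval.

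Most of this stands as a limit on the size of the point. A reader might also take section 9.7.8 as an admission that site effects are expected, because it mentions "interviewer bias, either by systematic differences in data recording or different interpretation of information on exposure or outcome for different patients". It does not go that far: it lists biases the data may suffer from, and speaks of patients, not sites.

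Two parts do not stand. Leaving details to the SAP does not settle the matter, because 9.7.4 already names the interval and 9.5 already prints the widths. And a descriptive study whose sample size rests on precision alone still needs an interval with its stated coverage.

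**Conclusion.** The planned interval and Table 3 omit between-site variation. This rests on the protocol's own text; the size rests on an assumed ICC and on sites being a sample from a wider population. Up to ICC about 0.02 nothing of practical weight is lost. At 0.05 to 0.10 coverage falls to about 92.5% and 90%, and the exact interval is short by about 0.014 to 0.029 (0.154 − 0.140; 0.169 − 0.140). A finite-population view shrinks this. If the requirement of a baseline score above 1 reduces the evaluable patients per site further, the effect softens again.

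Two stronger readings are tempting and unsupported. One is that the interval is too narrow whenever sites differ: the exact interval is slightly conservative and still covers about 95% at ICC 0.01. The other is that 300 patients are too few: the overall width stays below 0.20 throughout the range up to ICC 0.10. The claim with little room is the one for 105-patient subgroups. This is a cheap improvement, not a flaw that overturns the design.

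**What to change.** In 9.7.4, report the primary rate with a site-cluster-robust logit 95% CI, using a t quantile with (number of sites − 1) degrees of freedom, at least beside the exact CI, and report the observed ICC. The site number is already in the patient code.

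In 9.5, recompute Table 3 and the subgroup statement with the method to be used, over a range such as ICC 0, 0.01, 0.05 and 0.10.

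In the simulation, the logit interval with a t quantile covers 95.0 to 95.5% at every ICC tried. It is no wider than the exact interval when sites do not differ (0.139 against 0.140). An exact interval on the effective sample size (Korn-Graubard) is less attractive: even at ICC 0 it is about 7% wider (0.149) and covers 97%.

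The cost is wording in 9.5, 9.7.4 and the SAP, with no new data and no more patients. The interval becomes somewhat wider if sites differ and is practically unchanged if they do not. The change does not turn purposively chosen sites into a probability sample of German practice, so the caveat in 9.2.6 should stay.

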9.7.5 Analysis of secondary outcome(s)

- Change of pain over time: The responses to each of the BPI-SF items and the following two dimensions which are aggregated from BPI-SF items will be summarized descriptively:
 - Pain severity index:

It uses the sum of the four items on the pain intensity. All four severity items must be completed for aggregating the pain severity index.
 - Pain interference index:

It uses the sum of the seven pain interference items. The pain interference index is scored as the mean of the item scores multiplied by seven, given that at least four of the seven items have been completed.

Summary statistics, including mean and change from baseline, will be provided for each assessment time point. For the summary of each post-baseline assessment, patients will be excluded if there is no corresponding post-baseline measurement.

- For bone pain related quality of life assessment summary statistics including mean and change from baseline will be provided for each assessment time point of the FACT-BP questionnaire. For the summary of each post-baseline assessment, patients will be excluded if there is no corresponding post-baseline measurement.
- Pain control rate will be summarized. Pain control is defined as no increase by two or more points from the baseline measurement of the ‘Worst Pain’-item of the BPI-SF (Question 3) at any post-baseline assessment.
- Pain progression rate will be summarized. Pain progression is defined as two or more points increase from the baseline measurement of the ‘Worst Pain’-item of the BPI-SF (Question 3) at any post-baseline assessment.
- Time to first pain progression will be summarized by Kaplan-Meier (KM) estimates.
- Pain response will be additionally summarized descriptively for the subgroups defined in ‘evaluation of covariates on pain response’ in Section 9.1.2.

An analysis of covariance model will be used to assess changes in pain severity, as measured by the worst pain score on the BPI-SF, at each post-baseline assessment time point. The baseline worst pain score will be used as a covariate in each analysis of covariance model.

- The relation between bone uptake in known lesions and pain palliation will be analyzed (only in patients with bone scan prior to start of treatment and at least one further documented bone scan during or after end of Radium-223 treatment).
- The course of blood counts will be analyzed. Incidence of blood counts below limit for further injections according to the local product information in patients with different extent of disease

and in the whole patient population will be calculated. The incidence proportion will be provided, along with the exact 95% confidence interval.

- Time to event variables (TTNT, SSE, OS) will be summarized using Kaplan-Meier estimates. Median event times together with the 25th and 75th percentiles and associated 95% confidence intervals will be presented. Censoring rules will be defined in the SAP.
- Incidence of treatment emergent and drug-related AEs will be presented using the NCI-CTCAE Version 4.03. Additional subcategories will be based on event intensity and relationship to study drug.

Further details will be given in the SAP.

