9.1.2 Secondary endpoint(s)

The secondary endpoints are:

- **Changes of pain over time** by evaluating the worst pain item as well as the subscale scores for pain severity and pain interference as determined by patient responses on the BPI-SF questionnaire. The worst pain item and subscales will be presented separately for each post-baseline assessment.
- **Changes in bone pain related quality of life** as determined by patient responses on the bone pain specific FACT-BP questionnaire. The FACT-BP score will be presented separately for each post-baseline assessment.
- **Pain control rate** as determined by the worst pain item on the BPI-SF patient questionnaire. Pain control is defined as no increase by two points from the baseline BPI-SF worst pain score.
- **Pain progression rate** as determined by the worst pain item on the BPI-SF patient questionnaire. Pain progression is defined as an increase by two points from the baseline BPI-SF worst pain score at any post baseline assessment.
- **Time to first pain progression** is defined as the time between the first injection of Radium-223 until an increase in the BPI-SF worst pain item by at least two points.
- **Time to first opioid use** in patients who did not take opioids at study entry is defined as the time from first injection of Radium-223 until first intake of opioid analgesics.
- **Evaluation of covariates on pain response** of mCRPC patients during treatment with Radium-223. The following covariates will be analyzed:
 - opioid use
 - assessment of extent of bone metastases (<6, 6-20, > 20, superscan)
 - location of bone metastases
 - level of alkaline phosphatase at baseline (<150 mU/l, 150-300 mU/l, and >300 mU/l)
 - PSA level at baseline (<50 µg/l, 50-200 µg/l, and >200 µg/l)
 - WHO pain score at baseline (WHO-Score 0+1 and WHO-Score 2+3)
 - pretreatment with chemotherapy (yes/no)
 - pretreatment with deep androgen ablation by treatment with abiraterone or enzalutamide (yes/no)
 - extent of bone uptake in known lesions (only faint, higher uptake, and strong uptake compared to surrounding bone)

- **Relation between bone uptake in known lesions and pain palliation** (only in patients with bone scan prior to start of treatment and a second scan during or within 6 weeks after end of Radium-223 treatment)
- For **Radium-223 treatment patterns** dosage and number of injections of Radium-223 will be analyzed.

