9.3.1 Variables to determine the primary endpoint(s)

The variables for primary objectives are:

- Pain severity will be measured using the worst pain score of the BPI-SF questionnaire. The BPI-SF will be administered prior to each injection of Radium-223 and, if within routine clinical practice, at a follow-up visit approximately one month after the last injection of Radium-223.

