9.7 Data analysis

9.7.1 Statistical considerations

Statistical analyses will be primarily of explorative and descriptive nature.

All statistical details including calculated variables and proposed format and content of tables will be detailed in the Statistical Analysis Plan (SAP). The SAP will be finalized before study database lock. The SAP is available upon request (see Table 4: List of stand-alone documents, Annex 1).

Patients receiving at least one dose of Radium-223 will be considered valid for safety analysis set.

Analyses of pain or QoL will be performed for patients with evaluable patient questionnaires (BPI-SF, FACT-BP, respectively) at baseline and at least one post baseline visit. A clinically increase or decrease in opioid use will be taken into account. E. g. all patients without opioid intake as well as patients taking opioids will be included in analyses until an increase in opioid intake. Further details will be defined in the SAP.

Other analyses will be performed for the safety analysis set unless otherwise defined.

Whenever reasonable, data will be stratified by subgroups (i.e. age, other baseline characteristics).

All therapies documented will be coded using the World Health Organization – Drug Dictionary (WHO-DD). Medical history, any diseases and AEs will be coded using the latest Medical Dictionary for Regulatory Activities (MedDRA) version.

It is planned to have one interim analysis at the time of 6 months after LPFV. This analysis will use uncleaned data and will primarily focus on pain and QoL assessment. The final analysis will be performed after end of the study which is the date the analytical dataset is completely available.

9.7.2 Analysis of demography, disease details, prior and concomitant medication and other baseline data

Demography and baseline characteristics will be described with summary statistics. Concomitant medication will be coded using WHO's drug dictionary.

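### The pain control rate counts every patient without a recorded two-point rise as controlled, however short his follow-up, so early death or stopping raises it and lowers the progression rate

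*Protocol*

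**What the plan says.** Section 9.1.2 of the protocol gives the endpoint without a time frame: "Pain control is defined as no increase by two points from the baseline BPI-SF worst pain score". Section 9.7.5 repeats it with a slightly fuller threshold, "Pain control is defined as no increase by two or more points from the baseline measurement of the" worst-pain item, and adds that this applies to any post-baseline assessment. The next bullet defines the mirror image: "Pain progression is defined as two or more points increase from the baseline measurement of the" same item, again at any post-baseline assessment. Both rates are simply to be summarized.

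The pain analyses take in "patients with evaluable patient questionnaires (BPI-SF, FACT-BP, respectively) at baseline and at least one post baseline visit" (9.7.1). On timing, 9.3.1 says: "The BPI-SF will be administered prior to each injection of Radium-223 and, if within routine clinical practice, at a follow-up visit" about one month after the last injection. The long-term follow-up listed in 9.2.7 and Table 2 contains no BPI-SF.

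Two further statements bear on the point. Section 9.7.5 plans Kaplan-Meier estimates for time to first pain progression, which is the same two-point event. Section 9.7.1 gives, as an example of how opioid use will be handled, that "all patients without opioid intake as well as patients taking opioids will be included in analyses until an increase in opioid intake".

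**The concern.** Read naturally, a patient is controlled if none of his obtained forms shows a two-point rise. Nothing in the definition asks how many forms there were or over what period control had to hold. Since the forms end with treatment, a patient who dies or stops early supplies few of them, stays in the denominator, and receives the favourable score by default.

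Both rates then depend on how long patients stay on treatment as well as on their pain. That matters for two uses the protocol foresees: comparison with historical clinical data (9.9), and analysis of secondary outcomes by baseline factors (9.7.8). A group that loses more patients early would look better controlled for that reason alone. If observation is also cut at an opioid increase, as in the 9.7.1 example, it may be shortened in patients whose pain is worsening.

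**Working it through.** **The plan's own figure.** The protocol states no precision for pain control. Its only precision figure is Table 3, for pain response with 300 × 0.70 = 210 evaluable patients. The interval p ± 1.96·√(p(1−p)/210) reproduces it: p = 0.70 gives 0.638 to 0.762, width 0.124; p = 0.50 gives 0.432 to 0.568, width 0.135 (stated 0.136, the difference of the rounded limits). The half-width is therefore about 6 to 7 points, a useful yardstick if a similar number is evaluable for control.

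**Direction.** Suppose a patient shows no rise on his first m forms. One more form either leaves him controlled or removes him from that group; it can never turn a progressed patient into a controlled one. The control rate can only fall, and the progression rate only rise, as forms are added. This needs no assumption about rates.

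**Size: inputs.**
- Up to six post-baseline forms: five before injections 2 to 6 and one follow-up form. Six injections is the course described for the earlier phase III trial in section 7, assumed here.
- q, the risk of a first two-point rise at each assessment: not in the protocol; assumed 5%, 8% and 12%.
- d, the probability of leaving (death or stopping) after each assessment: not in the protocol; assumed 5%, 10% and 15%, unrelated to pain.

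**Size: formulas.** P(m forms) = (1−d)^(m−1)·d for m = 1 to 5, and (1−d)^5 for m = 6. A patient with m forms is scored controlled with probability (1−q)^m. The rate as defined is Σ P(m)·(1−q)^m; the rate with all six forms is (1−q)^6.

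**Size: worked case, q = 8%, d = 10%.**
- P(m): 0.100, 0.090, 0.081, 0.073, 0.066, 0.590.
- 0.92^m: 0.920, 0.846, 0.779, 0.716, 0.659, 0.606.
- Sum of products: 0.092 + 0.076 + 0.063 + 0.052 + 0.043 + 0.358 = 0.685 (from unrounded terms).
- With all six forms: 0.606. Difference: about 8 points.
- Standard error at n = 210: √(0.685 × 0.315/210) = 0.032.

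| q | d | Rate as defined | All six forms | Difference (points) |
|---|---|---|---|---|
| 5% | 5% | 76.4% | 73.5% | 2.9 |
| 8% | 10% | 68.5% | 60.6% | 7.8 |
| 12% | 15% | 60.7% | 46.4% | 14.3 |

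Differences come from unrounded values. A wider grid (q 5-15%, d 10-20%) gives 5.5 to 20 points. If those who leave would afterwards have had twice the risk, that grid gives about 10 to 32 points.

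**Is early loss plausible?** Section 7 quotes a median survival of 14.9 months for the earlier trial's radium-223 arm. With S(t) = exp(−ln2·(t/14.9)^k) and t in months, deaths between weeks 4 and 24 are 0.958 − 0.773, about 18% (k = 1), or 0.989 − 0.855 = 13% (k = 1.5). These figures are background only and do not enter the table.

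**The case against.** The strongest reply is that the plan already handles unequal follow-up: the same two-point event gets a Kaplan-Meier analysis in 9.7.5, timed from first injection. That stands in part. It gives the reader a progression estimate that allows for differing observation, provided censoring is unrelated to pain. It does not alter the control and progression rates, which are separate secondary objectives in 8.2. For the same reason, a reader should not infer that the plan ignores follow-up time altogether.

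A second reply is that derivation rules belong in the SAP, to which 9.7.1 and 9.7.5 defer. A SAP, not available here, could add a landmark or a minimum number of forms. But the definition and the one-form entry rule are already fixed in the protocol and produce the bias as they stand. The only deferral specific to censoring covers time to next treatment, skeletal events and survival.

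Third, control might be reported visit by visit, as 9.7.4 does for response; the crediting over time would then not arise. The control bullet does not say so, and the rule in 9.7.5 that drops patients without a form is attached to the score summaries. The alternative reading remains possible, however, and is one more reason to settle the wording.

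Finally, the stakes are limited. This is a descriptive secondary rate in a single-arm study with no test attached, 9.7.8 acknowledges bias from loss to follow-up, and 9.9 warns about historical comparison. That bears on priority and does not remove the bias.

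**Conclusion.** The point holds for the pain control rate and, in mirror image, the pain progression rate. Under the natural reading, in which control means no rise on any obtained form, the direction is certain. The size is not: about 3 to 14 points over assumed progression risks of 5-12% per assessment and leaving rates of 5-15% per interval, with six forms and leaving unrelated to pain. Across most of that range the shift exceeds the standard error of about 3 points at n = 210.

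Three stronger readings are tempting and not supported. Patients with no post-baseline form are not scored as controlled; 9.7.1 leaves them out. No particular inflation can be claimed for this study, because the protocol gives neither rate and the benchmark is a hypothetical in which everyone, including those who die, completes six forms. In the worked case, the 36% who are controlled on all six forms (the 0.358 term) are not the true control rate; that figure answers a different, composite question.

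**What to change.** In 9.1.2 and 9.7.5:

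- Report pain progression as cumulative incidence at a stated time from first injection, with death as a competing event, extending the planned time-to-progression analysis. Choose a time within the period of pre-injection forms. On a six-injection, four-weekly course those end at about week 20; the form at about week 24 is collected only where the follow-up visit is routine, so requiring it would penalise patients whose site does not hold that visit. Use actual form dates, since 9.2.7 sets no exact visit dates.
- Report pain control at each assessment with an explicit denominator, showing separately patients controlled, progressed, dead, stopped treatment, and form missing.
- Keep the crude any-assessment rate as a supplement, next to the number of forms per patient.

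No new data are needed: forms, injection dates, opioid use and date of death are already collected. The cost is revised wording, one more table, and a control rate that will look less favourable. Cumulative incidence still assumes that patients who stop treatment alive resemble those who continue, which is why the separate line for stopping is needed.
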